4.3 Subject Recruitment, Enrollment and Screening

4.3.1 Subject Recruitment

Several resources will be utilized for recruitment of potential subjects including:

- from within the clinical and referral practices of both [name] (regulatory sponsor and MCR site PI) in Rochester and [name] (MUSC site PI) and [name] (MUSC site Co-I) in South Carolina
- referrals from other care providers within the treatment communities
- radio advertisements
- invitation letters sent to parents of potentially eligible patients
- print advertisements, including but not limited to brochures, flyers, Craigslist, and listings in research classifieds
- trial listing with ClinicalTrials.gov
- trial listing on SCResearch.org

- trial listing on MCR and MUSC research websites

All advertising materials will be reviewed and approved by appropriate site IRB prior to use.

Potentially interested adolescents and their families may be provided with printed patient educational materials to aid them in making an informed decision regarding their willingness to participate in this study. These include the Mayo Clinic educational materials “Is transcranial magnetic stimulation right for me?” and “Transcranial Magnetic Stimulation (TMS)”. (See Appendix L for copies)

4.3.2 Subject Enrollment

At the time of the enrollment visit, potential subjects and their parent(s) will be provided with a written copy of the current IRB-approved informed consent/assent form from the site at which they will be receiving study treatments (Appendices H and I). All adolescents and their guardians will be provided a careful assent and consent discussion prior to enrollment. Due to the nature of a sham-controlled trial, all participants will need to understand that during Phase I of the trial, they will be randomized to either the active treatment condition or the sham treatment condition. They will also be informed about the opportunity to receive open, active rTMS treatment during Phase II if they did not have clinical response during Phase I. For subjects who reach the age of majority (18 years at both sites), written consent will be obtained from the subject at the next visit following their birth date.

4.3.3 Subject Screening

Following the informed consent process, enrolled subjects will begin the study eligibility screening process. The Eligibility Checklist and Verification CRF will be used at both sites to ensure that the subject is eligible for the study and that it is safe for them to participate. See Appendix E for comprehensive list of assessments used during screening to ensure eligibility.

Urine drug sample and, for females, urine pregnancy sample will be collected; subjects will not be initiated on any imaging protocol or rTMS treatment prior to these results becoming available and confirmed as negative for pregnancy and all nonprescribed substances of abuse.

4.4 Early Withdrawal of Subjects

4.4.1 When and How to Withdraw Subjects

Subjects will be withdrawn from the study immediately if a seizure, DSM-IV-confirmed treatment-induced mania, or other UADE occurs. Subjects will also be withdrawn from the study, at the time of notification of study staff, if at any point they meet any of the exclusionary criteria outlined in protocol Section 4.2.

Subjects enrolled in Maintenance Treatment (Arm 2) in Phase II will be withdrawn from the study if they experience a worsening of their depression. Worsening of depression will be defined as a CDRS-R score increase of >33% of Phase II baseline or a raw CDRS-R score of ≥ 40 , whichever occurs first, accompanied by clinician determination of significant

clinical deterioration as noted by a clinical global improvement (CGI-I) scale score of ≥ 6 (much worse or very much worse). Worsening of suicidal ideation and behavior will be defined as an increase of the Columbia – Suicide Severity Rating Scale (C-SSRS) suicidal ideation score of ≥ 4 or suicidal behavior including actual suicide attempts, interrupted/aborted attempts, or preparatory acts or behavior. These subjects will be referred to the care of their primary clinician or psychiatric provider. Subjects and families will be given recommendations for alternative treatment options and will be offered care through the clinic. There are no funds to pay for psychiatric hospitalization of a subject in this study; however, research staff and physicians will be available at all times to evaluate subjects with adverse behavioral consequences and, if necessary, arrange for admission to a local hospital.

Subjects may decide to withdraw from the study at any time, for any reason, including inability to tolerate study treatment, lack of improvement of depressive symptoms, or worsening of depressive symptoms. There are no currently-known risks associated with abrupt discontinuation of treatment with rTMS.

Subjects will be encouraged to remain compliant with all prescribed medications and expected study visits. Nonadherence to expected study visits and/or medications will be documented and may result in removal from the study. This will be clearly discussed during the consent/assent process and reinforced throughout the study through regular screening for changes in medications or issues with compliance.

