A resuscitation cart including an Ambu bag and oxygen will be available in the treatment suite. Furthermore, a clinician trained in seizure management will observe all rTMS sessions. All individuals acting as the on-site seizure management clinician will be required to demonstrate this capacity to the regulatory sponsor. In the event of a seizure, the primary en suite clinician will initiate appropriate clinical care as defined within the clinical rTMS practice. In management of seizures, attention must be taken to minimize

the risk of aspiration, and when possible guiding the patient into the left lateral decubitus position is desirable. Because most seizures are brief (typically <60 seconds) and without serious physical sequelae, efforts will be focused on preventing complications of the seizure rather than initiating any specific medication that is not required unless a seizure is prolonged. If a prolonged seizure (>60 seconds) is identified, appropriate response measures will be initiated which may include notifying a hospital-based pediatric rapid response team (Mayo Clinic site), following approved MUSC policies pertaining to medical events in "Non-clinical areas", and/or escorting patient to the nearest emergency department upon stabilization. The patient may be provided lorazepam (or equivalent benzodiazepine available in the resuscitation cart) to abort the seizure. To date, status epilepticus has never been described following rTMS.

If a seizure occurs during the active treatment phase of the study, active treatment as part of the study will be discontinued. Ongoing monitoring of mood and neurocognitive symptoms per the study protocol will be offered.

Any seizure event during the study will be reported as follows:

MUSC will report to the regulatory sponsor ([name]) and reviewing IRB per policy.

The regulatory sponsor and MCR site PI will report to the DSMB, reviewing IRBs, Neuronetics, and FDA as required per agreements, regulations, and policies.

Mood considerations

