Suspected treatment-induced mania will be evaluated using the Young Mania Rating Scale (YMRS). A YMRS score of ≥ 20 will prompt administration of the Schedule for Affective Disorders and Schizophrenia for School Aged Children (K-SADS) - Affective Disorders Supplement, to establish whether the patient meets the Diagnostic and Statistical Manual of Mental Disorders, Fourth Edition (DSM-IV) criteria for mania. A YMRS score of 20 or greater will be considered an adverse event (AE) and will be monitored using the YMRS; the emergence of DSM-IV-verified mania will be treated as a serious adverse event (SAE) and will also be monitored using the YMRS.

Management plan for treatment-emergent mania, exacerbation of depression, and/or suicidality

During the consent process, subjects and families will be educated about the possibility of significant changes in mood, suicidal thinking, and/or behaviors during the treatment. These changes could include emergence of mania, worsening of depression, and/or suicidal thinking and behaviors. Both the adolescent and parent(s) will be told to initiate contact with their study doctor, either [name] (MCR) or [name] (MUSC), if they experience any significant mood or behavior changes including suicidal ideation. Principal Investigator contact information is included in each site's consent/assent document. See Appendices H and I for drafts. Furthermore, during the active treatment phases of the protocol, subjects will have clinician interactions 5 days/week where changes of psychological symptoms will be queried (see Tables 4-6 for schedules of assessments). Ongoing monitoring for worsening of depression and emergence of suicidal ideation and/or behaviors will be evaluated using the CDRS-R, C-SSRS, CGI-I, and CGI-S.

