Some youth with depression will encounter crises. Most crisis management involves a combination of case management and creative problem solving, which can be accomplished within the framework of the existing treatment. If any treatment-related SAE occurs, including verified treatment-emergent mania, hypomania, exacerbation of depression, and/or worsening of suicidality, the subject, their guardian/parent, and their primary treating physician will be notified of this development, and a discussion as to the most appropriate clinical course of action will occur. This will include an offer to discontinue the rTMS treatment course, withdrawal from the study, and may include the need to seek emergent psychiatric stabilization (including hospitalization).

This protocol will follow the procedures of the American Academy of Child and Adolescent Psychiatry (AACAP) Practice Parameters on Suicidal Behavior.[\[18\]](#) These parameters indicate that subjects should be referred for hospitalization if their condition is unstable as manifested by suicidal ideation with inability to contract for safety, psychosis, current intoxication, mania, rapid cycling, or mixed state. Social factors that may cause the clinician to consider hospitalization include lack of sufficient environmental support and structure to guarantee the child's safety. Subjects and families will be given recommendations for alternative treatment options and will be offered care through the clinic. There are no funds to pay for clinical care outside the parameters of the study or for psychiatric hospitalization of a subject in this study; however, research staff and physicians will be available at all times to evaluate subjects with adverse behavioral consequences and, if necessary, arrange for admission to a local hospital.

Other potential side effects of rTMS that may be experienced during treatment

Some patients treated with rTMS have reported experiencing discomfort due to stimulation of the scalp musculature under the site of stimulation. A muscle tension headache may result in some patients that can persist for 1-2 hours post stimulation; however, these headaches typically respond to symptomatic treatment. In fact, recent findings suggest the possibility that chronic headache sufferers had mitigation of headaches during the course of treatment and upon follow-up (Wall, Baruth, Croarkin, et al. Submitted 2012). See Appendix C1 for copy.

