4.4.2 Data Collection and Follow-up for Withdrawn Subjects

To enhance the validity of study data, as well as to provide subjects with ongoing monitoring and safety assessments by a qualified professional, subjects who choose to withdraw from the interventional portion of the study will be offered the opportunity to complete mood, cognitive, safety, and imaging assessments as per the study protocol.

5 Study Device

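### Sections 4.4.1 and 1.4.2 give different consequences for a seizure and for verified mania, and Section 4.4.2 does not clearly give subjects withdrawn by rule the scheduled assessments through six months

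*Combined protocol and SAP*

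**What the plan says.** Section 4.4.1 (When and How to Withdraw Subjects) is mandatory and concerns the study, not only the treatment: "Subjects will be withdrawn from the study immediately if a seizure, DSM-IV-confirmed treatment-induced mania, or other UADE occurs". It also withdraws anyone who later meets an exclusion criterion of Section 4.2, and Phase II Arm 2 subjects whose depression worsens as defined there.

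Section 1.4.2 (Anticipated Risks) deals with the same two events:

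- Seizure: "If a seizure occurs during the active treatment phase of the study, active treatment as part of the study will be discontinued". It continues: "Ongoing monitoring of mood and neurocognitive symptoms per the study protocol will be offered".
- Verified mania: "the emergence of DSM-IV-verified mania will be treated as a serious adverse event (SAE) and will also be monitored using the YMRS". The management plan then begins "If any treatment-related SAE occurs, including verified treatment-emergent mania" and describes a discussion of the clinical course with the family and treating physician. Of that discussion it says: "This will include an offer to discontinue the rTMS treatment course, withdrawal from the study".

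Section 8.5 (Stopping Rules) refers the reader to 1.4.2 for the occasions on which treatment may be stopped. It does not mention 4.4.1.

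Section 4.4.2 is headed as covering withdrawn subjects in general, but its offer reads "subjects who choose to withdraw from the interventional portion of the study will be offered the opportunity", followed by mood, cognitive, safety and imaging assessments per protocol.

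**The concern.** Two questions need one answer each: what happens to the subject's treatment, and what happens to the subject's follow-up. For verified mania the protocol gives two answers to the first question. For a seizure it gives two answers to the second. The two sites could each follow the text and still handle the same event differently.

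What is at stake is safety follow-up. The primary safety endpoint (Section 3.4) runs through the six-month follow-up period. The secondary safety endpoint (Section 3.5) compares cognitive scores with baseline after the final treatment and again six months later. If a subject withdrawn by rule is treated as having left the study, the later scheduled assessments may not take place, and this would affect subjects withdrawn because something went wrong.

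**Working it through.** This is a comparison of texts. Arithmetic serves only to size it.

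**1. Consequence of each event**

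| Event | Section 4.4.1 | Section 1.4.2 | Where they differ |
|---|---|---|---|
| Seizure | Immediate withdrawal from the study | Study treatment stops; per-protocol mood and neurocognitive monitoring is offered | Treatment stops under both. They differ on whether the subject remains in the study for assessment |
| DSM-IV-confirmed mania | Immediate withdrawal from the study | Classed as an SAE, monitored with the YMRS, discussion including an offer to discontinue | Mandatory removal against an offer |

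The stop-and-monitor rule is written only for seizure. The offer clause names mania, and would reach a seizure only if the seizure counts as a treatment-related SAE. YMRS monitoring after mania does not in itself conflict with withdrawal, because adverse events are followed afterwards in any case.

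**2. Follow-up of a subject withdrawn under 4.4.1**

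- Exit assessment: provided. Section 6.2 has mood and cognitive assessments for all subjects at early withdrawal. Section 6.2.8 schedules the visit within 5 business days of notification, and Table 4 footnote g agrees.
- Adverse events: provided. Section 8.1 follows unresolved events and sets a six-month period after the last rTMS. Section 8.2 follows ongoing, probably related SAEs to outcome.
- Scheduled mood, cognitive and safety assessments through the six-month visit: offered after a seizure by 1.4.2. Section 4.4.2 offers them to those who choose to withdraw. Section 6.2.8 assigns the later Phase I visits to those electing not to enter Phase II. None of these names a subject removed for mania, a UADE, a newly met exclusion criterion or Arm 2 worsening.
- Contrast: Section 5.4 withdraws Phase I subjects who cannot keep the schedule from the treatment portion only, and expressly offers them ongoing assessments. The distinction is therefore drawn there but not carried into 4.4.1 and 4.4.2.

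**3. Size**

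Seizure rate in 1.4.2: 1 in 30,000 treatments. Expected number = treatments / 30,000; chance of at least one = 1 − (1 − 1/30,000)^n.

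- Phase I active: 38 × 30 = 1,140 treatments; 1,140 / 30,000 = 0.038 expected; chance of any 3.7%.
- Upper case, everyone entering Phase II Arm 1: 38 × 60 + 37 × 30 = 3,390 active treatments; 0.113 expected; chance of any 10.7%.

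The documents give no rate for mania or for the other 4.4.1 triggers.

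Power for the binary response (Section 7.1: 65% against 25%, 35 per group, two-sided 0.05), with p̄ = 0.45:

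Φ{[0.40 − 1.96 √(2 × 0.45 × 0.55 / n)] / √[(0.65 × 0.35 + 0.25 × 0.75) / n]}

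- n = 35: Φ[(0.40 − 0.2331) / 0.1089] = Φ(1.53) = 93.7%, against 94% stated, so the plan's figure reproduces.
- n = 34: 93.1%. n = 32: 91.5%.

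Losing one to three subjects per group outright would thus barely matter. Under the planned LOCF analysis they would not be lost.

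**The case against.** The best defence is that the conflict is loose terminology. Treatment stops after a seizure under either section. Section 4.4.2, despite its heading, speaks of leaving the interventional portion, so withdrawal in 4.4.1 could be read the same way, and then the seizure texts agree. For mania, 4.4.1 could be taken as the specific rule, and the clause in 1.4.2 as a general one covering several outcomes. The grammar of that clause also leaves open whether study withdrawal is part of the offer or a separate step.

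For seizure much of this stands: the question is one of study status, not treatment. For mania it does not settle the matter. Section 1.4.2 names verified mania, and Section 8.5 directs the reader to 1.4.2 alone. An ambiguous sentence is itself a reason to rewrite.

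The defence also rightly blocks several stronger inferences:

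- A reader might infer that subjects withdrawn by rule drop out of follow-up altogether. The exit visit, the adverse event follow-up and the post-seizure offer show otherwise.
- A reader might infer that each seizure or mania is a primary safety endpoint case that would be lost. The triggering event is already recorded when it occurs. Nor is it clearly an endpoint case: Section 8.1 restricts a UADE to effects not previously identified in the plan, 1.4.2 identifies both events, and Section 8 lists mania among expected events that are not UADEs. The word 'other' in 4.4.1 points the opposite way, so their status is at most unclear.
- A reader might infer that such withdrawals would fall mainly on the active arm and bias the LOCF analysis. The documents give no rates by arm, and the value carried forward would normally be the exit rating.

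**Conclusion.** The point holds in a limited form. Sections 4.4.1 and 1.4.2 state conflicting consequences: substantively for verified mania, and as to study status for seizure. Section 8.5 does not resolve either. Section 4.4.2 leaves subjects removed under 4.4.1 without a clear entitlement to scheduled assessments through six months, apart from the post-seizure offer.

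The effect on power and on the primary efficacy analysis is negligible. The value of the change lies in uniform conduct across the sites and in complete six-month mood, cognitive and safety data. The seizure count assumes that the labelled device rate applies to adolescents and that all 38 active subjects receive 30 treatments. How often the other triggers would occur cannot be judged from the documents. The point merits an amendment, but it does not threaten the trial's main conclusion.

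**What to change.** - Reconcile Sections 1.4.2, 4.4.1, 4.4.2 and 8.5 so that each event has one stated consequence, and have 8.5 refer to 4.4.1 as well. Which clinical rule applies is for the sponsor and clinicians; no view is taken here.
- Define stopping study treatment and leaving the study as separate states, and use the terms consistently.
- Reword 4.4.2 so that the offer of scheduled mood, cognitive, safety and imaging assessments, through the six-month visit, covers every subject who stops treatment, by choice or by rule, unless consent is withdrawn. The Phase I wording in Section 5.4 is a usable model.

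The cost is amendment text and a few assessments that are already on the schedule. No change to sample size or analysis is needed.

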4.4.2 Data Collection and Follow-up for Withdrawn Subjects

To enhance the validity of study data, as well as to provide subjects with ongoing monitoring and safety assessments by a qualified professional, subjects who choose to withdraw from the interventional portion of the study will be offered the opportunity to complete mood, cognitive, safety, and imaging assessments as per the study protocol.

5 Study Device

5.1 Description

The NeuroStar TMS Therapy® System is a computerized electromechanical instrument that produces and delivers brief duration, rapidly alternating (pulsed) magnetic fields to induce electrical currents in localized regions of the cerebral cortex. It is a non-invasive tool used for the treatment of patients with MDD who have not achieved clinical response from one prior adequate trial of antidepressant pharmacotherapy (see Appendix J3 for detailed product description and use). The NeuroStar TMS Therapy™ System has been FDA-approved for use in adult patients. NeuroStar XPLOR™ is a clinical research option for the NeuroStar TMS Therapy System that provides features necessary to conduct randomized, controlled trials and other TMS research. Active treatment modality is essentially the same for both the NeuroStar TMS Therapy™ System and NeuroStar XPLOR™. See Appendix J4 for description of NeuroStar XPLOR device.

The NeuroStar XPLOR TMS System consists of the following equipment and software:

- Mobile Console (includes processor module, power module, mast, gantry, halo, and display arm)
- System Software; the XPLOR option also includes a dedicated system software

- application (software version 1.7.5 or greater) with its own dedicated database of patient/subject treatment history, TrakStar application, and TrakStar database that operates only with the corresponding XPLOR Software, maintaining isolation, security, and data integrity of the research
- Practice Data Management System (PDMS) software
 - Therapy Coils; included with the XPLOR option is a set of three TMS coils:
 - a blinded sham or placebo coil; the sham coil is acoustically matched to protect the integrity of the blind,
 - a blinded active coil, and
 - a standard treatment coil that can be used for performing motor threshold level determination or open-label treatment.
 - Head Support System (includes laser positioning aid and coil positioning guide)
 - Treatment Chair
 - Positioning Cushions (to enhance comfort and positioning of the patient in the required posture for the duration of the treatment session)

The NeuroStar TMS System also requires supplies and disposables for each treatment session:

- Head Cushion Liner
- Head Side Pad Liner
- Head Positioning Straps
- Earplugs
- SenStar Treatment Link (a single-use medical device)
- Used SenStar Treatment Link Return Box

5.2 Method for Assigning Subjects to Treatment Groups

Enrolled subjects will be assigned to either the blinded sham coil or the blinded active coil during Phase I of the study using a permuted block randomization method, with the result of the same number of subjects being assigned to both treatment groups. The randomization schedule will be generated by the Mayo Clinic Health Sciences Research (HSR) Biostatistical team. Once generated, the randomization assignment for each subject receiving treatment will be printed on a separate card and sealed in an envelope prepared by the HSR team. These envelopes will be unsealed and subjects will be randomized to the study prior to their first treatment, but not before informed consent/assent has been obtained, they are confirmed to be eligible for the study, and all baseline visit requirements have been fulfilled. In this way, selection bias can be avoided should study staff deduce the nature of the blinded coils. For safety precautions, the full randomization schedule will be sent to the chair of the Data Safety Monitoring Board by the HSR team. In addition, study staff will keep a spreadsheet of the subject number associated with each randomization number, so that the DSMB may unblind a specific subject in the event of a medical emergency.

The XPLOR software has built-in checks that, once a subject has been randomized to a particular coil, will prevent treatment from taking place with the incorrect blinded coil. This safety precaution provides blinding to the staff applying study treatment, staff performing the mood, cognitive, safety, and imaging assessments, and to the subjects – essentially creating a triple-blinded procedure.

